The treatment options available to patients with PNH differ significantly by country and geographical region. The current standard of care (SOC) for PNH involves complement inhibition, which has significantly improved patient outcomes. Allogeneic hematopoietic stem cell transplantation (HSCT) is a curative option that is available in certain countries but presents significant risks. In countries where complement inhibitors are not currently available, management of patients is mainly through supportive care (Cançado et al. 2021).

Crovalimab, a novel, long-acting monoclonal antibody (mAb) targeting C5, has demonstrated efficacy in reducing hemolysis, improving QoL, and potentially offers a more convenient dosing schedule compared to existing therapies (eculizumab and ravulizumab). Overall, crovalimab has shown a well-tolerated safety profile, similar to that of eculizumab in patients with PNH, both in treatment naïve patients and in patients already on treatment with eculizumab or ravulizumab (Roth et al. 2025; Roth et al. 2024).

However, as crovalimab is a new treatment, comprehensive post-marketing surveillance is essential to fully understand its long-term safety profile and potential risks. This is particularly important given the chronic nature of PNH and the need for long-term treatment.

The most commonly reported adverse events (AEs) with crovalimab treatment are pyrexia, headache, infections, infusion and injection-related reactions (IRRs), injection-related reactions (only affecting crovalimab SC administration) and transient immune complex reaction (TICR), also known as Type III hypersensitivity reaction (affecting only patients switching treatments). Meningococcal infection is an important AE of crovalimab treatment, related to its mode of action.

The European Medicines Agency (EMA) and the U.S. Food and Drug Administration (FDA) have requested additional data on specific safety concerns, including:

- Serious infections: Complement inhibition can increase the risk of infections.

- Meningococcal infections: Infections caused by encapsulated bacteria are of special interest, as patients treated with the current SOC have very high-risk to encapsulate infections.
- Hemolysis after discontinuation: The potential for rebound hemolysis upon treatment cessation is high. Nevertheless, the likelihood that a patient with PNH will discontinue treatment with a complement inhibitor without switching to another similar treatment is low.

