9.2.3 Participant Follow-up

The follow-up period will be the time period from index date (as defined in Section 9.2.1) until the end of the study or censoring, whichever comes first.

To evaluate AESIs and other AEs and SAEs for all participants with PNH, the date of censoring will be defined as the earliest occurrence of any of the following events:

- Consent withdrawal
- Site termination
- Crovalimab treatment discontinuation¹ (with an extra follow-up period after discontinuation)
- Enrollment into an interventional clinical trial²
- Death

To assess safety events during pregnancy and breastfeeding, including pregnancy and infant outcomes, additional censoring events will be defined:

- Date of delivery (for pregnancy safety and outcomes)
- First year of the infant's life (for safety and infant outcomes)
- On the date when breastfeeding stops or first year of the infant's life (for breastfeeding)

[figure not shown]
¹ For participants with PNH censored due to crovalimab treatment discontinuation, follow-up will continue up to 12 months if the participant does not start a new complement inhibitor or for 12 weeks if the participant starts a new complement inhibitor.

² To preserve the integrity of data collected for any interventional therapy for PNH in clinical studies, as well as to avoid duplicate safety reporting, participant data collection will be paused from the Crovalimab Silo and the Core Registry when participants enroll in an interventional clinical study for a PNH therapy.

Note: Safety events from the mother will continue to be recorded even after pregnancy ends, delivery, or the cessation of breastfeeding. Similarly, infant safety events will also continue to be recorded through their first year of age if breastfeeding is suspended.

Evaluation of pregnancy and infant outcomes during crovalimab exposure will rely on prospectively collected data within the Crovalimab Silo only for participants who enroll into the silo before being pregnant. However, for participants who enroll into the Crovalimab Silo while being pregnant, retrospective data on crovalimab exposure and outcomes will be incorporated into the silo, if such data are available from the Core Registry. Data for participants whose pregnancy outcomes occur before their enrollment in the Crovalimab Silo will not be obtainable. Very few instances are expected in these latter two scenarios due to the timing of drug approvals and site initiations in the Core Registry (see Figure 3).

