9.3 VARIABLES

9.3.1 Variables for All Participants with PNH

9.3.1.1 Crovalimab Exposure

The Crovalimab Silo is an observational study. No study medication will be provided as part of participation. Dosing and treatment duration of crovalimab are at the discretion of the physician in accordance with local clinical practice and local labeling.

Crovalimab exposure will be defined as the duration from the date of silo enrollment until crovalimab discontinuation date, plus 12 months if the participant with PNH does not start a new complement inhibitor or plus 12 weeks if the participant starts a new complement inhibitor. For participants with PNH who enroll into the silo under crovalimab treatment, additional time under crovalimab previous to enrollment will be

evaluated from available data requested at enrollment or from the Core Registry at baseline. Dates of exposure to crovalimab and doses administered will be collected and characterized.

For pregnancy and infant outcomes, exposure is defined as the period from 9 months (Based on the average estimated crovalimab terminal half-life of 53.1 days reported in the studies of crovalimab) prior to the DOC until the date of delivery. For breastfeeding outcomes, exposure is defined as the duration from 9 months previous the start of breastfeeding until the infant's first birthday or the date breastfeeding ends, whichever comes first.

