Obstetric history ^g	X		
Pregnancy status, outcome and maternal complications	X	X	X
AEs, adverse fetal/neonatal/infant outcomes and baby complications, including growth and development deficiency ^h		X	X
Breastfeeding information	X	X	X
Vaccination	X	X	X
Fatigue questionnaire ⁱ	X	X	

Data	Baseline (Enrollment Visit) ^a	Follow-up ^b	Participant Discontinuation of Crovalimab/Registr y Completion ^c
------	---	------------------------	--

AE = adverse event; ASEI = adverse event of special interest; FACIT = Functional Assessment of Chronic Illness Therapy; LDH = lactate dehydrogenase; MAVE = major adverse vascular event; PNH = paroxysmal nocturnal hemoglobinuria; SAE = serious adverse event; ULN = upper limit of normal.

- ^a Data from baseline will include information collected in the core and at the enrollment visit.
- ^b Data are expected to be entered in the electronic data capture system approximately every 6 months post-enrollment. Every participant will be followed up during their entire crovalimab treatment and up to 12 months after discontinuation of crovalimab, if they do not start a new complement inhibitor (or 12 weeks if they start a new complement inhibitor).
- ^c After discontinuation from crovalimab, participants with PNH would be followed up for 12 months from the discontinuation date of crovalimab (if they do not start a new complement inhibitor) or up to 12 weeks after discontinuation (if they start a new complement inhibitor).
- ^d Including serious infections, Meningococcal infection, development or worsening of any neurological condition (e.g., axonal neuropathy, multifocal mononeuropathy, etc.), malignancies and hematologic abnormalities, serious hemolysis in participants with PNH who discontinue crovalimab, transient immune complex reactions, and infusion and injection related reactions. Treatment, hospitalizations, outcomes and causality for AESIs, AEs, and SAEs will be also collected.
- ^e Including, but not limited to MAVEs (including thrombosis), packed red blood cell transfusions, breakthrough hemolysis, high disease activity status (evidence of $LDH \geq 1.5 \times ULN$ with any of the following symptoms: fatigue, hemoglobinuria, abdominal pain, shortness of breath, anemia (hemoglobin < 100 g/L), dysphagia, erectile dysfunction, development or worsening of autoimmune disease, bone marrow pathology and hematological disorders, impaired renal function, impaired hepatic function, and death.

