9.7.1 Safety Analyses

No formal statistical testing will be performed. Descriptive statistics will be reported using summary tables and figures (where appropriate). Continuous variables will be summarized using mean, standard deviation, median, range (min–max) and interquartile range. Categorical variables will be summarized using counts and proportions (%).

Additionally, incidence and incidence rate (IRs; in person-years) and their 95% CIs of AESIs, SAEs and AEs will be calculated. The exact 95% CIs will be computed using the Clopper-Pearson method (Clopper and Pearson 1934). For the calculation of IRs, the denominator will be the pooled person-time of all the participants within the cohort. The patient time–at-risk will be calculated from index date until the date of an incident event or censoring, whichever occurs first. All first events occurring during follow-up period will be counted in the total number of events (thus, for each participant, only the first event will be counted) and divided by the total patient-years at risk. In addition, to IRs, incidence proportions will be calculated as proportion of participants with PNH afflicted with each of the AESIs, SAEs, and AEs up to the data extraction date.

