9.7.2 Subgroup and Sensitivity Analyses

Subgroup and sensitivity analyses will be implemented when sample size allows.

Analyses will be presented separately for all participants with PNH, for pregnant female participants with PNH, for all infants, and for infants sub-grouped by breastfeeding status (yes/no).

When feasible, analyses will be further detailed according to each trimester of pregnancy and each quarter within the infant's first year of development.

To account for previous complement inhibitor exposure, subgroup analyses will be also based on previous PNH treatment exposure, using the following definitions: "naïve new users" when individuals initiate crovalimab without prior exposure to C5 inhibitors, and "Prevalent new users" when individuals initiate crovalimab after having received at least one C5 inhibitor any time prior to crovalimab treatment start. Safety events will be also described by causality.

Potential confounding factors influencing safety and pregnancy outcomes, such as demographic information (e.g., age, race/ethnicity), clinical characteristics, maternal medical history, obstetrical history, comorbidities, and concomitant medications will be described among participants with PNH who experience an AESI, as well as for pregnancy or infant outcomes. If needed, subgroup analysis will be performed and AESIs proportions and incidence rates will be compared between subgroups.

Similarly, subgroup analysis may include clinical and laboratory test outcomes for PNH (e.g., MAVEs, HDA, BTH, etc.) and previous PNH treatment.

Sensitivity analysis will be performed restricting the data to safety events and crovalimab exposure that was collected prospectively only. The effects of the timing of crovalimab exposure before and during pregnancy and cumulative exposure periods on each outcome will be also evaluated as sensitivity analysis. Sensitivity analysis may also include timing variations of FTT and development deficiency outcomes, when available.

Full details on all statistical analyses, including other subgroup and sensitivity analyses, will be described in the Statistical Analysis Plan (SAP).

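### A participant who stops crovalimab for a stem cell transplant and starts no complement inhibitor stays in crovalimab exposure for up to 12 months, so post-transplant infections and malignancies enter the AESI rates

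*Protocol*

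**What the plan says.** Protocol Section 9.2.3 lists five censoring events for the all-participant AESI, AE and SAE analyses: consent withdrawal, site termination, crovalimab discontinuation, entry into an interventional trial, and death. The discontinuation item comes "with an extra follow-up period after discontinuation". Footnote 1 fixes the length of that period by one question. Either "follow-up will continue up to 12 months if the participant does not start a new complement inhibitor", or it continues "for 12 weeks if the participant starts a new complement inhibitor".

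Section 9.3.1.1 builds the same tail into the exposure definition, which runs to the discontinuation date "plus 12 months if the participant with PNH does not start a new complement inhibitor". The notes to Table 1 in Section 9.3.3 repeat the rule for data collection: "up to 12 months after discontinuation of crovalimab, if they do not start a new complement inhibitor".

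Section 9.7.1 states the counting rule: "All first events occurring during follow-up period will be counted in the total number of events". It has no causality condition. Section 9.7.2 adds only this: "Safety events will be also described by causality".

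On transplant, Section 7 says: "Allogeneic hematopoietic stem cell transplantation (HSCT) is a curative option that is available in certain countries but presents significant risks". HSCT is not mentioned in the censoring list, the exposure definition, the subgroup and sensitivity analyses, or Table 1.

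**The concern.** The rule already accepts that later PNH treatment can blur attribution. A new complement inhibitor cuts the tail to 12 weeks, and entry into an interventional PNH trial pauses data collection. HSCT is the other treatment that the protocol singles out for its risks, and it changes nothing. Because HSCT is not a complement inhibitor, a transplanted participant who starts none gets the longest tail available.

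Three of the seven primary AESI categories could then include events that arise from transplant rather than from crovalimab: serious infections, meningococcal and other encapsulated infections, and malignancies. They would be reported as frequencies under crovalimab exposure. The push is upward, and it could differ between countries because access to transplant does.

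**Working it through.** **Inputs from the protocol.** Planned N = 300 with up to 7 years of follow-up (Section 9.5). Serious infection in 6% of crovalimab trial patients and no meningococcal infection or serious hemolysis (Section 9.5). Terminal half-life 53.1 days (Section 9.3.1.1). Tails of 12 months and 12 weeks (Section 9.2.3). The protocol gives neither the number of transplants nor the infection risk after transplant. Both are assumptions below.

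**Step 1: the plan's own figures.** Table 2 follows from 1 - (1 - p)^300. At p = 0.5% this gives 77.8%, at 1.0% 95.1%, at 1.5% 98.9% and at 2.0% 99.8%, as printed. The point rests on the follow-up and counting rules, not on Table 2.

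**Step 2: trace one participant.**
- Crovalimab is stopped for HSCT and no complement inhibitor follows, so Section 9.2.3 gives up to 12 months.
- HSCT is not a censoring event, so follow-up is not cut.
- Section 9.3.1.1 labels those months crovalimab exposure.
- A first serious infection in month 3 after HSCT falls in follow-up and is counted under Section 9.7.1.
- If the clinician assesses it as not related, Section 9.7.2 shows it that way, but it stays in the rate.

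**Step 3: a rare AESI.** With no other case in 300 participants, the exact (Clopper-Pearson) limits are:
- 0/300: upper limit 1 - 0.025^(1/300) = 1.22%.
- 1/300: estimate 0.33%, 95% CI 0.01-1.84%.

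A single post-transplant case turns a zero into a non-zero estimate and raises the upper limit by about half (1.84/1.22 = 1.5).

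**Step 4: a common AESI.** Let h be the number transplanted, q the added risk of a serious infection in the tail, and b the baseline proportion. The excess in first-event cases is h × (1 - b) × q. With b = 6%, the baseline is 0.06 × 300 = 18 cases. For q = 0.3 to 0.8:

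| h (assumed) | Expected cases | Percent |
|---|---|---|
| 1 | 18.3-18.8 | 6.1-6.3 |
| 3 | 18.8-20.3 | 6.3-6.8 |
| 6 | 19.7-22.5 | 6.6-7.5 |
| 9 | 20.5-24.8 | 6.8-8.3 |

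The highest cell adds 9 × 0.94 × 0.8 = 6.8 cases, or 38% of 18. That ratio sets transplants accrued over up to 7 years against a trial proportion whose follow-up time is not stated. If the registry baseline were 2 to 4 times the trial figure (assumed; 36 to 72 cases), the same cell would add 9 × 0.88 × 0.8 = 6.3 of 36 (18%) or 9 × 0.76 × 0.8 = 5.5 of 72 (8%). All cells in the table lie inside the exact 95% CI for 18/300 (3.6-9.3%).

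**Step 5: person-time.** Each transplant adds at most 1 person-year. With h = 1 to 9 and mean follow-up of 3 to 6.25 years (assumed), the share is 1/(300 × 6.25) = 0.05% to 9/(300 × 3) = 1.0%. The distortion comes through the event count, not the denominator.

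**Step 6: residual drug.** 84/53.1 = 1.6 half-lives leaves 33% at 12 weeks. 365.25/53.1 = 6.9 half-lives leaves 0.8% at 12 months. Early post-transplant events can still reflect crovalimab. Late ones hardly can.

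**The case against.** The strongest reply is rarity. Section 7 expects few patients to stop a complement inhibitor without switching to a similar treatment, and transplant recipients are only part of that group. Section 7 also says HSCT is available only in certain countries. No section predicts that any of the 300 will be transplanted. This stands, and it limits the effect on common AESIs.

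A second reply is that all-cause counting is the stated design, and that the causality definitions in Section 11.1 let clinicians assign such events to underlying disease or concurrent treatment. That is true of the display. It does not give a rate without those events.

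A third is that the SAP can deal with it. In part it can, but the protocol itself fixes the censoring list and the end of exposure. Table 1 lists concomitant medication and last PNH treatment at baseline only. Its follow-up items are open-ended but do not name HSCT, so the date needed for a later repair is not assured.

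Stronger readings are tempting, and the documents do not support them:
- A reader might infer that post-transplant cytopenias will be counted. The AESI name includes hematologic abnormalities, but Section 9.3.1.2.4 describes only malignancy, so this is not established.
- A reader might infer a serious-infection count inflated by a third or more. That needs transplant numbers and risks found nowhere in the protocol, and a baseline on a different time scale (Step 4).
- A reader might conclude that follow-up should simply end at the start of conditioning. That would drop early events while crovalimab persists, and would leave transplant recipients with no tail while switchers keep 12 weeks.

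Two groups escape the 12-month tail: participants who start another complement inhibitor around transplant, and those who enter an interventional PNH trial.

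**Conclusion.** The point holds. Followed as written, Sections 9.2.3, 9.3.1.1 and 9.7.1 put first serious infections, encapsulated infections and malignancies after HSCT into the crovalimab AESI rates, and nothing in Section 9.7.2 takes them out or shows rates without them. It applies only to participants who stop crovalimab for HSCT and start no complement inhibitor.

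The effect on common AESIs is likely small, because such participants are probably few. No firm figure can be given, since transplant frequency and post-transplant risk are not in the protocol. For rare AESIs one event is enough to matter: 0/300 (95% CI 0-1.22%) becomes 1/300 (0.01-1.84%). No printed figure is wrong. The gap is in the follow-up rule, and it is cheap to close before data accrue.

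**What to change.** - Record the HSCT date during follow-up, from the Core Registry if it is held there, otherwise in one eCRF field, and add it to Table 1.
- In Sections 9.2.3, 9.3.1.1 and 9.7.2, split person-time and events at HSCT.
- Report AESI, SAE and AE rates censored at HSCT alongside the rates over the full tail as now defined.
- List post-HSCT events separately, with time since the last crovalimab dose.

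This is a change to analysis and data collection only and does not touch treatment. The cost is one date field and one added set of rates. Neither the Core Registry fields nor the eCRF is shown, so whether the date is already collected needs checking. The downside is that events soon after transplant that may reflect residual crovalimab appear only in the full-tail rates and the listing, which is why both sets of rates are needed.

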9.2.2 Inclusion/Exclusion Criteria

To evaluate AESIs and other SAEs and AEs for all participants with PNH:

Participants with PNH included in the SDU study will meet the same inclusion and exclusion criteria from the Crovalimab Silo listed below:

- Inclusion criteria:
 - Participants with PNH confirmed by flow cytometry.
 - Participant and/or parent/legally authorized representative provide written informed consent/assent to participate in the Core Registry and the Crovalimab Silo prior to any registry-related data collection, in a manner approved by the Institutional Review Board (IRB)/Independent Ethics Committee (IEC) and local regulations.
 - Participants with PNH currently being treated with or who start crovalimab during the study period.
- Exclusion criteria:
 - Participants with PNH participating in an interventional PNH clinical trial while receiving crovalimab (i.e., in combination with other therapy), with exception of

participants with PNH participating in the extension period of COMMODORE/COMPOSER Roche studies and Post Trial Access Programs.

The exclusion criteria for all participants will also be applicable to assess crovalimab exposure during pregnancy, as well as pregnancy, infant, and breastfeeding outcomes.

To evaluate AEs and SAEs during pregnancy and pregnancy outcomes:

The following additional inclusion criteria will be applicable:

- Crovalimab exposure during pregnancy or 9 months before DOC

To evaluate infant AEs and SAEs and infant and breastfeeding outcomes:

The following additional inclusion criteria will be applicable:

- Breastfeeding infant
- Infant younger than 12 months of age

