9.3.2.1.19 Maternal Death

Maternal death is defined as the death of a pregnant woman during pregnancy, labor, or delivery. Maternal deaths for up to 12 weeks after delivery will also be reported.

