In real-world clinical practice, treatment switching is common for various personal or medical reasons. Furthermore, the potential for loss to follow-up (including death, registry participation or consent withdrawal) and variations in the standard of care (SOC) across different countries can also preclude the possibility of maintaining a minimum 5 –year follow-up for all participants with PNH.

The MAH will proactively consider renegotiation with the IPG registry if required to extend the Crovalimab Silo primary data collection study duration, depending on enrollment of pregnant participants with PNH and participant follow up. Consistent with the commitment to obtaining pregnancy safety data, participant recruitment and follow-

up progress will be closely monitored, and updates will be provided as part of interim reports. In parallel, the MAH will investigate alternative approaches for data collection to supplement enrollment, if needed.

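### A pregnancy counts as exposed up to 9 months after crovalimab, but follow-up can end 12 weeks after a switch with no pregnancy exception, and the infant-year text conflicts

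*Protocol*

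**What the plan says.** **Who counts as exposed.** Section 9.2.2 admits a pregnancy on this criterion: "Crovalimab exposure during pregnancy or 9 months before DOC". Section 9.3.1.1 uses the same window to define exposure for pregnancy and infant outcomes and gives its basis: "Based on the average estimated crovalimab terminal half-life of 53.1 days reported in the studies of crovalimab".

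**When follow-up ends.** Section 9.2.3 censors at the earliest of several events. One is crovalimab discontinuation plus an extra period, which is 12 months when no other such drug follows. The shorter limit, for a switch, reads: "or for 12 weeks if the participant starts a new complement inhibitor". For pregnancy, infant and breastfeeding outcomes it says that "additional censoring events will be defined": delivery, the infant's first year, and the end of breastfeeding. Table 1, footnote b, repeats the general limit: "Every participant will be followed up during their entire crovalimab treatment and up to 12 months after discontinuation of crovalimab", with 12 weeks for those who switch. Footnote c counts both periods from the discontinuation date. Neither footnote mentions pregnancy.

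**What is promised for infants.** Section 8.2 sets a primary objective that runs through at least the first year of life. Table 1 footnote h, attached to the infant row, says the same. Section 9.2 gives infants their own index date, birth.

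**The concern.** The exposure window and the follow-up window were set separately and do not fit together. A woman can qualify for the pregnancy cohort through exposure that ended months before conception, or through exposure early in pregnancy before a switch. The follow-up rule can then remove her before the outcome is known.

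The loss depends on when exposure occurred. Preconception or early-pregnancy exposure followed by a switch is cut off, while exposure up to delivery is not. Section 9.7.2 plans to evaluate the timing of exposure before and during pregnancy, so this loss falls on the very contrast it wants to describe. The cohort is small: Section 9.5 aims for about 25 pregnant participants. Outcomes may also be hard to recover later, because Section 9.9.8 says the data-sharing agreements prevent access to other silos, where a switched woman's later data may sit.

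For infants, a site that reads Table 1 cannot tell whether footnotes b and c or footnote h governs once the mother has stopped or switched.

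**Working it through.** **Inputs**
- Qualifying window before conception: 9 months (Section 9.2.2) = 9 × 30.4375 / 7 = 39.1 weeks.
- Follow-up after discontinuation: 12 weeks with a switch; 12 months = 365.25 / 7 = 52.2 weeks without one (Section 9.2.3; Table 1 footnotes b and c).
- Conception to delivery: 38 weeks at term. This is an assumption, not in the protocol; 35 weeks is also shown.
- The discontinuation date is taken as the end of exposure, also an assumption.

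**The plan's own figure.** The 9 months follow from the half-life if five half-lives are meant (the multiple is my assumption): 5 × 53.1 = 265.5 days; 265.5 / 30.4375 = 8.7 months, rounded to 9.

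**Delivery.** It is observed only if stop date + follow-up period ≥ conception + time to delivery. The latest stop that still loses delivery therefore falls just before (time to delivery − follow-up period), counted from conception.

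| Case | 38 weeks to delivery | 35 weeks to delivery |
|---|---|---|
| Switch (12 weeks) | 38 − 12 = 26 weeks after conception, about gestational week 28 | 35 − 12 = 23 weeks, about gestational week 25 |
| No switch (52.2 weeks) | 38 − 52.2 = −14.2 weeks, about 3.3 months before conception | 35 − 52.2 = −17.2 weeks, about 4.0 months before conception |

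Gestational week is taken as weeks from conception plus 2. A switcher loses delivery if she switched before the stated point. A non-switcher loses it only if she stopped before the stated point; any stop in pregnancy without a switch still captures delivery.

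**Conception itself.** A switch more than 12 weeks before conception ends follow-up before the pregnancy exists, although the pregnancy would qualify for a further 39.1 − 12 = 27.1 weeks.

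**Early loss.** Section 9.3.2.1.2 defines spontaneous abortion as loss before 20 weeks. A switch at gestational week 8 or later gives follow-up to at least 8 + 12 = week 20, so that outcome is covered.

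**Infant year, if the mother's limit applied to the infant.** Without a switch, 12 months reach the first birthday only if she stops at or after delivery. With a switch, she would have to stop at infant age 12 − 84/30.4375 = 12 − 2.8 = 9.2 months or later. These figures show what footnotes b and c would do if they governed; the protocol does not say that they do.

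**Full coverage.** To reach delivery for every qualifying pregnancy, follow-up from last exposure would need 39.1 + 38 = 77.1 weeks, or 17.7 months. The first birthday would need 29.7 months.

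**The case against.** **Infants.** A reader might infer that the protocol cuts off the infant's first year whenever the mother stops before delivery. The text does not say so. Infants have their own index date and censoring event, Table 1 footnote h promises at least a year, and the discontinuation footnote in Section 9.2.3 speaks of participants with PNH. This objection stands: for infants there is a contradiction to resolve, not a stated rule of early censoring.

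**Mothers.** It can be argued that the pregnancy censoring events replace the general list, since each list opens with its own purpose. The wording "additional censoring events will be defined" points the other way. A replacement would also leave the pregnancy analyses with no censoring for death, consent withdrawal or site termination. The note in Section 9.2.3 continues maternal recording after pregnancy, delivery or breastfeeding ends, but does not mention stopping crovalimab.

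**Frequency.** Section 9.9.4 calls stopping entirely in pregnancy unlikely, and Section 7 says the same of discontinuing without switching. That makes the 12-month limit rarely important, but it also means that women who leave crovalimab mostly fall under the 12-week limit. Section 9.5 says "treatment switching is common for various personal or medical reasons", though in explaining why five-year follow-up may fail, not about pregnancy. It would be tempting to say that 69% (27.1 / 39.1) of preconception switches are lost before conception. That is a share of calendar dates; the protocol gives no distribution of stop dates, so it says nothing about the share of women. Nor do the documents show that switches follow pregnancy complications.

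**Maternal death.** Censoring at delivery might seem to clash with Section 9.3.2.1.19: "Maternal deaths for up to 12 weeks after delivery will also be reported". The note in 9.2.3 and that sentence largely settle it.

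**Feasibility.** This study uses secondary data. Finding every conception after a stop or switch would mean tracking all such women for 9 months, which is not cheap and may run into the silo limits of Section 9.9.8. This stands, and it narrows the fix.

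**Conclusion.** The concern holds in a limited form. The exposure definition and the follow-up limits do not match for women who leave crovalimab before or during pregnancy, and the protocol states no exception for them. Assuming 38 weeks to delivery, a switch before about gestational week 28 ends follow-up before a term delivery (about week 25 if delivery comes at 35 weeks). Without a switch, delivery is lost only for stops more than about 3.3 months before conception (4.0 months on the 35-week assumption). For infants, the one-year promise and footnotes b and c have to be reconciled.

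Women who stay on crovalimab through delivery and the infant's first year are unaffected. The number of pregnancies lost cannot be estimated from the protocol, but with about 25 planned, each one counts.

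**What to change.** In Section 9.2.3 and Table 1 (footnotes b, c and h):

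- State that, for any pregnancy meeting the Section 9.2.2 exposure criterion and known to the registry before the discontinuation limit is reached, stopping crovalimab or starting another complement inhibitor does not end observation of the pregnancy outcome or of the infant to 12 months.
- Flag exposure to another complement inhibitor after a switch as a descriptor.
- Keep pregnancies whose outcome cannot be obtained in the denominator, reported as outcome unknown.
- For conceptions after follow-up has ended, state in Section 9.9 that the 9-month preconception window is only partly observable, especially after a switch.

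The cost is protocol wording, a few extra eCRF entries, and a data transfer agreement that covers these records. Some outcomes will carry co-exposure after a switch. This is an observation rule and changes no treatment.
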